16.2.2.2 Logistic regression

Certain binary outcome variables, e.g. response outcomes, will be evaluated using a logistic regression model. The model will include factors and covariates as specified for respective analysis. The SAS code below outlines a template for the analysis where covariates can be added or removed as required:

```
ods output diff=lsm_diff convergencestatus=conv_status;
proc logistic data=;
by visit;
class treatment strata / param=glm;
model response = treatment strata weight;
lsmeans treatment / diff cl exp;
run;
```

In cases where separation is a concern, e.g. 0% or 100% response for some treatment and covariate level combination, an exact logistic regression model may be applied to all visits. To help with convergence, this model will not include any continuous covariates. The SAS code below outlines a template for the analysis where covariates can be added or removed as required:

```
ods output exactoddsratio=exact_or;
proc logistic data=data exactonly;
by visit;
class treatment strata / param=ref;
model response = treatment strata;
exact treatment / estimate=odds;
run;
```

When exact logistic regression is unable to be implemented (due to computational complexity as the procedure can lead to extremely long run times), then Fisher's exact test will be applied. In this case, only a p-value for a test of equal response in the two groups can be obtained (no odds ratios or confidence intervals can be estimated.)

```
ods output fishersexact=fisher;
proc freq data=;
by visit;
table treatment*response / fisher;
run;
```

Input dataset should only contain data from the two treatment groups to be compared.

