4.2 Treatment groups

The summaries by treatment will primarily be performed by the randomized treatment but also by combination of randomized treatment and switch treatment. For some safety summaries (e.g. exposure-adjusted) the ‘switch’ treatment may be summarized separately.

- Randomized treatment:
 - AIN457 150 mg
 - Placebo
- Treatment sequence:
 - AIN457 150 mg
 - Placebo – AIN457 150 mg
- Switch treatments (for patients who cross-over):
 - AIN457 150 mg

5 Subgroup definitions

The primary and secondary endpoints will be analyzed by region (China and non-China). Analyses by previous use of TNF- α inhibitor will also be provided for total population and Chinese population.

6 Assessment windows, baseline and post baseline definitions, missing data handling

Baseline and post-baseline definitions

In general, a *baseline* value refers to the last measurement made prior to administration of the first dose of study treatment. A post-baseline value refers to a measurement taken after the first dose of study treatment.

Analysis visit windows

Analysis visit windows will be used for the data that is summarized by visit; they are based on the study evaluation schedule and comprise a set of days around the nominal visit day. For any assessment, there are protocol defined scheduled visits around which analysis visit windows were created to cover the complete range of days within the study. The analysis visit windows and rules for dealing with multiple measurements within the windows are described in [Appendix 16.1](#).

7 Subject disposition, background and demographic characteristics

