16.2.2 Analysis of binary and categorical data

16.2.2.1 Summary statistics for binary and categorical data

Summary statistics for discrete variables will be presented in contingency tables and will include count and frequency in each category. If applicable, confidence intervals will be derived as well based on the score method including continuity correction (Newcombe 1998):

With z as $(1-\alpha/2)$ -quantile of the standard normal distribution (SAS: $z=\text{probit}(1-\alpha/2)$, n as total number of subjects (i.e. number of subjects in the denominator), p as estimated crude incidence (number of subjects with event / n) and $q = 1-p$

Then the lower limit is

$$L = 100 \times \max \left(0, \frac{2np + z^2 - 1 - z\sqrt{z^2 + 2 - \frac{1}{n} + 4p(nq+1)}}{2(n+z^2)} \right)$$

and the upper limit is

$$U = 100 \times \min \left(1, \frac{2np + z^2 + 1 + z\sqrt{z^2 + 2 - \frac{1}{n} + 4p(nq-1)}}{2(n+z^2)} \right).$$

In addition, if $L > p$ then $L = p$ and if $U < p$ then $U = p$.

For binary response variables the placebo-adjusted response rates including 95% confidence interval will be derived.

SAS code for risk difference:

```
proc freq data=;
tables response*trt/ riskdiff;
run;
```

Note the response value should be sorted with ‘1’ ahead of ‘0’.

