The required analysis (e.g. ANCOVA) is then performed separately within each imputation dataset (as identified by variable *_imputation_*). To obtain the final result of the imputation process the analysis result from each imputation dataset needs to be combined according to Rubin’s rules as outlined below:

```
ods output parameterestimates=mi_result;  
proc mianalyze data=;
```

```
modeleffects estimate;  
stderr estimate_se;  
run;
```

The *estimate* and *estimate_se* parameters come from the analysis model used to analyze the imputed variable within each imputation dataset (e.g. from the lsmean estimate of the treatment difference and its standard error obtained from PROC LOGISTIC or PROC MIXED.)

To obtain binary response rates and confidence intervals for individual treatment groups the following process should be followed (exemplified for one visit):

```
ods output binomialprop=bin_est;  
proc freq data=;  
by treatment_imputation_;  
table response / binomial (cl=wilson correct);  
run;
```

Then apply a logit transformation on the saved proportions and derive its standard error:

```
data bin_est; set bin_est;  
estimate=log(_bin_/(1-_bin_));  
estimate_se=e_bin/_bin_*(1-_bin_));  
run;
```

The transformed binomial proportion estimates and its standard errors are then combined by applying Rubin's rules as described above using PROC MIANALYZE. Before presenting the combined data it needs to be transformed back as follows:

```
data mi_result; set mi_result;  
prop_est=1/(1+exp(-estimate));  
prop_lower=1/(1+exp(-lclmean));  
prop_upper=1/(1+exp(-uclmean));  
run;
```

If all responses are imputed as 0 (or 1) for all imputation datasets for a specific treatment group then the between-imputation-variation will be zero. The combined final response rate would be presented as seen in any of the imputed datasets but the 95% CI will be undefined.

If after imputation all responses are either 0 or 1 for a combination of treatment group and imputation dataset it will not be possible to perform a logit transformation and the response rate (0% or 100%) will be presented without 95% CI.

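### Could the SAP's logistic and imputed-rate SAS templates report reversed results because they name no response level or control arm?

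*SAP*

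**What the plan says.** SAP 11.4 defines the primary analysis as a logistic regression of ASAS20 response at Week 16, with odds ratios for secukinumab 150 mg relative to placebo. SAP 11.5 specifies the same model for ASAS40, ASAS 5/6 and partial remission. SAP 11.7 uses logistic regression for the ASQoL and SF-36 PCS responder analyses.

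The code outlines are in the SAP appendix:

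- **Main logistic template (16.2.2.2).** The model line is "model response = treatment strata weight" and the contrast is "lsmeans treatment / diff cl exp". Neither names an event level or a control arm.
- **Exact logistic template (16.2.2.2).** It uses "class treatment strata / param=ref" with no reference level named, and its model line names no event.
- **Imputed rates (16.2.3.1).** The purpose is stated as "To obtain binary response rates and confidence intervals for individual treatment groups the following process should be followed". The tabulation is "table response / binomial (cl=wilson correct", again with no level, and the result is carried through to "prop_est=1/(1+exp(-estimate".
- **Ordering note (16.2.2.1).** The one instruction on order begins "Note the response value should be sorted with" and asks for level 1 before level 0. It appears under the risk-difference code only.

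**The concern.** Response is coded 0/1. If the software takes the lowest ordered level as the event, the printed code models non-response. The odds ratio would then come out either as intended or as its reciprocal, depending on how the treatment variable sorts. The code for imputed rates would tabulate non-response and label it response, whatever the treatment coding.

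The main template serves the primary endpoint and three secondary endpoints, so the reported direction of effect would rest on a coding choice that the SAP does not state. The ordering note in 16.2.2.1 shows that the authors knew order matters, which makes its absence from the other templates look like an oversight.

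**Working it through.** **Inputs.** Response rates and group sizes of 300 and 150 come from SAP Table 15-1. The two-sided 5% level is in SAP 15. The anticipated drop-out of 10% at the primary endpoint is in Protocol section 4. The documents do not say which response level or arm the software takes by default, so all codings are shown.

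**1. The plan's own figures.** Full enumeration of two-sided Fisher's exact power at these rates gives more than 99.9% for ASAS20 (stated: about 99%), more than 99.9% for ASAS40 and ASAS 5/6 (stated: 99%), and 93.0% for partial remission (stated: 92%). The inputs are therefore being read as the plan reads them.

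**2. Odds ratio under each coding, ASAS20.** With event 1 and placebo as reference:

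OR = (0.611/0.389) / (0.284/0.716) = 1.571/0.397 = 3.96

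The Wald standard error of log OR, from expected counts 183.3, 116.7, 42.6 and 107.4, is √(1/183.3 + 1/116.7 + 1/42.6 + 1/107.4) = 0.216. The 95% CI is 2.59 to 6.05.

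| Event level | Comparison | OR |
|---|---|---|
| 1 | secukinumab vs placebo | 3.96 |
| 1 | placebo vs secukinumab | 0.25 |
| 0 | secukinumab vs placebo | 0.25 |
| 0 | placebo vs secukinumab | 3.96 |

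The result inverts only if exactly one setting is reversed; the inverted CI is 0.17 to 0.39. Suppose the defaults are the lowest level as event, and the first-sorted arm compared with the later one. Then labels sorting as listed in SAP 4.2 (active first) print 0.25, while 0/1 coding with placebo first prints 3.96. The documents do not settle which coding applies.

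**3. Other endpoints, intended and reciprocal.** ASAS40: 4.67 and 0.21. ASAS 5/6: 8.59 and 0.12. Partial remission: 3.78 and 0.26.

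**4. Effect on the tests.** Swapping the event level changes the sign of the treatment log odds ratio, and so does swapping the reference arm. Neither changes its standard error. A logistic fit to 183/300 against 43/150 responders, with simulated region and weight, gave 3.91 (2.56 to 5.97) or 0.256 (0.167 to 0.391) according to coding. In all four codings |z| = 6.307 and p = 2.8 × 10⁻¹⁰.

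**5. Imputed rates.** Tabulating level 0 would give 1 − 0.611 = 38.9% on secukinumab and 1 − 0.284 = 71.6% on placebo. This could not pass unnoticed. A responder under non-responder imputation remains a responder under multiple imputation, so the imputed rate cannot fall below the non-responder rate, and it can rise by at most the share with missing data. Treat the planning rates as the non-responder rates and take 10% missing in each arm. The imputed rate must then lie between 61.1% and 71.1% on secukinumab, and between 28.4% and 38.4% on placebo. Both 38.9% and 71.6% fall outside these limits.

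**6. Text against code.** The intended estimate is in the text: response as the outcome and secukinumab against placebo (11.4), and response rates by arm (16.2.3.1). The ANCOVA and MMRM templates in 16.2.1.2 also request differences with no control arm named, and leave the direction to the sentences that follow. The logistic templates follow the same convention.

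**The case for a change.** The best case for a change has four parts. First, the freedom the SAP gives in its templates concerns covariates; it says nothing about the event level or comparator. Second, elsewhere the SAP fixes a random seed and a sort order so that results can be reproduced, so the omission is out of keeping. Third, for the secondary endpoints the text speaks of a comparison between the two arms without saying which is the denominator, and SAP 11.7 is looser still. Fourth, the logistic contrast feeds the combination step of the multiple imputation, so an unset direction would carry through. The remedy is also only a few options in three templates.

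Much of this stands as description. The options are not printed, the ordering note is not repeated, and the arithmetic of a reversal is right. What does not stand is the step to a defect in the plan. Every adverse figure needs a software default and a dataset coding that the documents do not contain. The templates have blank dataset names and generic variables, so they cannot be read as the programs that will run. A program that printed non-response as response would depart from the SAP's own text. The exact model and the multiple imputation are also both optional.

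**Conclusion.** The omission is real but does not call for a change. The SAP states the estimates it wants, and leaving the direction to the text is its convention across model types. Hypotheses, p-values, type I error and power do not depend on the coding. The most that could go wrong is an inverted display: 0.25 in place of 3.96 for ASAS20, or 38.9% and 71.6% in place of 61.1% and 28.4%. Either would contradict the crude response rates by arm.

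That conclusion assumes that analysts take the outcome and comparator from SAP 11.4, 11.5 and 16.2.3.1, and that crude rates are reviewed alongside the model output. A programmer who wishes to print the options may do so, provided that the response level and the control arm are set together. Under the defaults assumed above with placebo sorted first, setting the event level alone would turn a correct 3.96 into 0.25.

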11.4 Analysis of primary variable

The primary efficacy variable is response to treatment according to the ASAS20 criteria at Week 16. The analysis of the primary variable will be based on the FAS patients.

Description

The ASAS Response Criteria (ASAS20) is defined as an improvement of $\geq 20\%$ and ≥ 1 unit on a scale of 10 in at least three of the four main domains and no worsening of $\geq 20\%$ and ≥ 1 unit on a scale of 10 in the remaining domain.

Statistical analyses

The statistical hypothesis for ASAS20 being tested is that there is no difference in the proportion of subjects fulfilling the ASAS20 criteria at Week 16 in secukinumab regimen versus placebo regimen.

Let p_0 denote the proportion of ASAS20 responders at Week 16 for Placebo regimen and p_1 denote the proportion of ASAS20 responders at Week 16 for Secukinumab 150 mg regimen,

In statistical terms, $H_0: p_1 = p_0$, $H_{A1}: p_1 \neq p_0$, i.e.

H_1 : Secukinumab 150 mg regimen is not different to placebo regimen with respect to ASAS20 response at Week 16

The primary analysis will be conducted via logistic regression with treatment, randomization stratum (region) as factors and baseline weight as a covariate. Odds ratios and 95% CI will be presented comparing secukinumab 150 mg regimen to placebo.

Supportive analyses

Sensitivity analyses and supportive analyses will be conducted in order to provide evidence that the results seen from the primary analysis are robust.

In order to determine the robustness of the logistic regression model used for the primary analysis, ASAS20 response at Week 16 will also be evaluated using a non-parametric

ANCOVA model ([Koch 1998](#)) with the same independent variables as the logistic regression model.

Interactions between treatment and selected baseline demographics and disease characteristics will be explored.

The impact of missing data on the analysis results of ASAS20 response will be assessed as well by repeating the logistic regression model using different ways to handle missing data. These may include, but are not limited to:

- Multiple imputation
- Observed data analysis

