16.2.4.2 Odds ratio and 100*(1- α)% confidence interval

For an investigational drug group with n_1 subjects at risk, independent from the control group (e.g. placebo or comparator) with n_0 subjects at risk, of whom x_1 and x_0 experience a certain event with probability π_1 and π_0 respectively, the odds ratio is estimated as

$\frac{p_1/(1-p_1)}{p_0/(1-p_0)}$ with $p_1=x_1/n_1$ and $p_0=x_0/n_0$. A conditional exact 100*(1- α)% confidence interval

can be obtained by using the SAS procedure PROC FREQ with statement EXACT OR. However, to be able to adjust for covariates odds ratios will primarily be obtained from PROC LOGISTIC.

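### SAP 16.2.2.2 wrongly says that no odds ratio or interval is available once Fisher's exact test is used; in that rare fall-back the promised odds ratio and the region stratum would be lost

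*SAP*

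**What the plan says.** SAP 16.2.2.2 sets out three steps for binary outcomes.

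1. The default is logistic regression on treatment, region and weight.
2. If separation is a concern, "an exact logistic regression model may be applied to all visits". Weight is dropped and region is kept: "model response = treatment strata".
3. The last step is reached "When exact logistic regression is unable to be implemented", for which the section cites computing time. The template is then "table treatment*response / fisher", with no region term, and the section remarks that "no odds ratios or confidence intervals can be estimated".

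Three other sections bear on that remark:

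- **SAP 16.2.4.2** says that a conditional exact interval for the odds ratio "can be obtained by using the SAS procedure PROC FREQ with statement EXACT OR". It adds: "However, to be able to adjust for covariates odds ratios will primarily be obtained from PROC LOGISTIC".
- **SAP 11.4** commits to an effect measure for ASAS20: "Odds ratios and 95% CI will be presented comparing secukinumab 150 mg regimen to placebo". SAP 11.5 makes the same commitment for ASAS40, ASAS 5/6 and ASAS partial remission.
- **SAP 16.2.2.1** plans, for binary response variables, the difference in response rates from placebo with a 95% CI, from an unstratified risk-difference call.

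**The concern.** The remark is a false statement inside a rule that programmers will follow. Fisher's test conditions on the margins of a two-by-two table. The conditional exact odds-ratio interval comes from the same conditional distribution, and 16.2.4.2 obtains it from the procedure that the Fisher template already calls. Read literally, 16.2.2.2 tells the programmer to leave out a quantity that 11.4 and 11.5 promise.

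The step also drops region without saying so. Region is the randomisation stratum (Protocol 3.1). It is in the planned logistic models for these four endpoints and in the exact model that Fisher would replace.

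At stake, for any output that reaches this step, are the odds ratio, its interval and the stratification by region.

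**Working it through.** The plan states no figure for this step. The check is therefore whether the quantities said to be unavailable exist, and how likely the step is to be reached.

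**Inputs.** 300 against 150 patients, 5% two-sided (SAP 15). Planning rates for partial remission, the sparsest tested binary endpoint, are 13.9% and 4.1% (SAP 15.1). About 80% of patients come from China (Protocol 3.1), so the strata are about 240/120 and 60/30. All responder counts below are assumed for illustration.

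**The plan's power figures.** Exact enumeration of Fisher's test gives more than 99.9% for ASAS20, ASAS40 and ASAS 5/6 (stated 99%), and 93.05% for partial remission (stated 92%). These agree closely enough, and nothing here disputes them.

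**Method.** Let T be the number of responders on active treatment and c_k its hypergeometric probabilities given the margins. For odds ratio ψ,

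P(T = k; ψ) = c_k ψ^k / Σ_j c_j ψ^j.

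The lower 95% limit solves P(T ≥ t; ψ) = 0.025 and the upper limit solves P(T ≤ t; ψ) = 0.025. If t is the largest possible value, the upper limit is infinite but the lower limit is finite. With region kept, c_k is the convolution of the two strata's hypergeometric distributions. This is the exact logistic model with treatment and a two-level stratum.

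**Pooled table**

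| Active vs placebo | Fisher p | Exact OR | Exact 95% CI |
|---|---|---|---|
| 42/300 vs 6/150 (near planning rates) | 0.0010 | 3.90 | 1.60 to 11.49 |
| 20/300 vs 1/150 | 0.0034 | 10.6 | 1.66 to 444 |
| 10/300 vs 0/150 | 0.035 | infinite | 1.14 to infinity |
| 42/300 vs 0/150 | 1.7e-8 | infinite | 6.20 to infinity |
| 5/300 vs 0/150 | 0.17 | infinite | 0.46 to infinity |

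An interval exists in every row, including those with no placebo responders.

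**With region kept**

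- 8/240 vs 0/120 and 2/60 vs 0/30: p = 0.035, 95% CI 1.14 to infinity, median-unbiased odds ratio 7.1.
- 34/240 vs 6/120 and 8/60 vs 0/30: odds ratio 3.89, 95% CI 1.59 to 11.48.

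Each calculation took about a millisecond in purpose-written code.

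**What 16.2.2.1 would still report** (Wald interval, d ± 1.96 √[p1(1−p1)/300 + p0(1−p0)/150])

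- 10/300 vs 0/150: 3.3 points (1.3 to 5.4).
- 20/300 vs 1/150: 6.0 points (2.9 to 9.1).
- 42/300 vs 6/150: 10.0 points (5.0 to 15.0).

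**How often the chain is entered.** At a 4.1% placebo rate, the chance of no partial-remission responder is 0.959^150 = 0.2% among all placebo patients. Among about 30 placebo patients outside China it is 0.959^30 = 28%, which matters for the region subgroup analyses of SAP 5. In the full-population model an empty cell in one region alone does not cause separation. These are chances of needing the exact model. Reaching Fisher requires that the exact model then also fails.

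**The case against.** The strongest case against is that the step will hardly ever be used, and that little is lost if it is.

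- **A reader might infer that affected endpoints would be reported by a p-value alone, with no effect size.** The documents do not support this. The response rates and risk difference of 16.2.2.1 do not depend on which test is used. Only the odds ratio, its interval and the stratification are lost.
- **A reader might infer that sparse partial remission, early visits or small subgroups lead to Fisher.** They lead to the exact logistic model, which keeps region and outputs an odds ratio. Sparse tables also make that model easier to compute. If it runs as fast as the check suggests, Fisher is not reached with the template as written.
- **A reader might infer that region is kept in every other analysis.** It is not. The convergence rule in SAP 16.2.1.2 can remove strata from the MMRM, and the risk-difference template in 16.2.2.1 is unstratified. In the 10/300 against 0/150 example, dropping region changes nothing visible.
- **The timing comes from purpose-written code, not from SAS**, and the templates allow covariates to be added. The run-time caution is therefore not shown to be wrong in general.
- **Section 16.2.4.2 stands under crude incidence and says only that the interval can be obtained.** It offers a method and makes no promise for this fall-back.

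All five limit the consequences. None of them rescues the remark. The wording of 16.2.4.2 is general and refers to the logistic-regression odds ratios, and the commitment to report odds ratios with intervals comes from 11.4 and 11.5.

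**Conclusion.** The point holds as a minor correction. The statement in 16.2.2.2 is false, conflicts with 16.2.4.2, and would break the reporting commitment of 11.4 and 11.5 wherever the step is used. The loss would be the odds ratio, its 95% CI and the adjustment for region.

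The step is a second fall-back and is unlikely at Week 16 in the full population. That judgement assumes the 4.1% planning rate for placebo partial remission and an exact model with only treatment and a two-level region factor. The primary test, alpha, power and sample size are untouched.

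**What to change.** Delete the parenthetical statement in SAP 16.2.2.2. Then choose one of the following:

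1. **Preferred.** Replace the pooled Fisher step with the exact conditional test and common odds ratio stratified by region, reported with the exact 95% CI.
2. **If pooled Fisher is kept.** Add the EXACT OR request of 16.2.4.2 to the template, report the conditional exact odds-ratio 95% CI beside the p-value, and label the result as unadjusted for region.

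The cost is one sentence and one code line in the SAP, with no new data. Some upper limits, and some point estimates, will print as infinite. A footnote should also say that Fisher's two-sided p and the equal-tailed exact interval can fall on opposite sides of 5%. For example, 8/60 against 0/30 gives p = 0.048 with an interval of 0.90 to infinity.
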